2.2. Rationale for Study Design

Although studies have evaluated optimal dwell time for Cysview fluorescence when cystoscopy is performed under blue light, the optimal dwell time for NIRF visualization has not been determined. Prior to conducting randomized studies comparing efficacy of NIRF and blue light we must first establish that a useful and short dwell time can in fact be used successfully. This pilot study will allow us to identify a dwell time for subsequent NIRF cystoscopy studies.

[figure not shown]
Because from a practical point of view, that is the longest time period we want to prolong surgery with a product that should equal or improve on current blue light cystoscopy. We use blue light very selectively now for these reasons: The Dwell study and the subsequent research that comes from it – should permit avoidance of the pre-op catheterization and significantly shorten the procedure. We have found ex-vivo the NIRF imaging is well over 10 times more sensitive to Cysview fluorescence and should have no problem with visualization at 10 minutes.

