5. METHODS AND STUDY PROCEDURES

The study will be a single center prospective nonrandomized trial of an investigational imaging technology. All patients will undergo investigational imaging and the concomitant standard of care, i.e. transurethral resection of bladder tumor (TURBT). Patients with suspected bladder cancer on cystoscopy will be enrolled to have subsequent intraoperative intravesical administration of Cysview and NIRF cystoscopy prior to TURBT.

Ten patients will be recruited to demonstrate the feasibility of using this NIRF imaging system at shorter intravesical instillation durations (Cysview™ dwell time). The instillation duration will be 10, 5, or 2.5 minutes in this patient series. The subject will be anesthetized, positioned, prepped, and draped for the white light TURBT. A catheter will be passed, Cysview instilled, and the catheter clamped for the assigned dwell time. It will then be unclamped after the dwell time designated, Cysview will be

allowed to drain out, the catheter removed, and cystoscopy performed. The cystoscope is inserted and imaging of the entire bladder commences while recording both color and near-infrared image streams (movies and periodic stills). This initial survey that includes catheterization of the bladder under anesthesia, instillation of Cysview, dwell time as indicated and subsequent evaluation with the color and near-infrared imaging for research purposes. Cysview with blue light cystoscopy has been indicated to be desirable at the time of TURBT but it is not standard of care; it is an optional procedure to increase detection and decrease recurrence. A useful dwell time for Cysview before NIRF imaging will be identified in this study; an effort will be made to minimize the interval between administration and imaging.

The procedure and all study portions will be performed by the subject's surgeon. During the procedure, the bladder will initially be examined in a systematic meridian fashion. Suspicious tumors identified by white light only, NIRF only, and both will be identified. If fluorescence is detected in 3/3 subjects at a given dwell time, the study will continue to shorter dwell times. The initial 3 subjects will have 10 min dwell duration, followed by 5 min and 2.5 min. If fluorescence is not detected in 3/3 subjects at any time period, the study will not progress to shorter dwell times. If no fluorescence is visualized after 10 minutes, we will not proceed to a longer dwell time.

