5.2. Efficacy Assessments

This initial series is designed solely to demonstrate that tumors identifiable under white light will be seen to fluoresce in the near-infrared spectrum after relatively short dwell times. We will document detectability of individual tumors under white light and NIRF at short intervals after Cysview instillation.

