8.3. Subject Enrollment/Randomization

Subjects will be assigned a drug dwell duration based upon the order of study entry. No randomization will occur. The first three study subjects will have a 10 minute dwell time. If the dwell time fluorescence is adequate, dwell time will be reduced to 5 minutes for the next three subjects and then 2.5 minutes accordingly.

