13. DATA ANALYSIS AND MONITORING

13.1. Sample Size Determination

Conventional blue light cystoscopy has a sensitivity of better than 0.9 (90%) for Ta-T4 tumors. Therefore, the probability that we will fail to detect the tumors in three subjects due to the sensitivity of the blue light method is less than 0.001 (0.1%). We thus believe that 3 subjects represent a sufficient sample size to determine the efficacy of this method.

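### Section 13.1 claims three subjects are enough to establish efficacy, using a probability that does not match the 3/3 progression rule; 3/3 supports feasibility only (exact two-sided 95% lower limit 29.2%)

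*Combined protocol and SAP*

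**What the plan says.** Section 13.1 holds the plan's only sample-size justification. It starts from another imaging method: "Conventional blue light cystoscopy has a sensitivity of better than 0.9 (90%) for Ta-T4 tumors". From this it derives a probability below 0.001 of failing to detect the tumors in three subjects, and concludes: "We thus believe that 3 subjects represent a sufficient sample size to determine the efficacy of this method".

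The rule that the three subjects feed is in Section 5: "If fluorescence is detected in 3/3 subjects at a given dwell time, the study will continue to shorter dwell times". Its companion sentence is: "If fluorescence is not detected in 3/3 subjects at any time period, the study will not progress to shorter dwell times". Section 8.3 sets the order of allocation, beginning with "The first three study subjects will have a 10 minute dwell time" and going on to 5 and then 2.5 minutes. It describes the condition for moving on as adequate fluorescence, without a count.

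On purpose, the primary aim in Section 1.1 is to find the shortest dwell time that gives adequate tumor detection. Section 2.2 adds: "This pilot study will allow us to identify a dwell time for subsequent NIRF cystoscopy studies". Section 5 speaks of feasibility, and Section 5.2 says the series is "designed solely to demonstrate that tumors identifiable under white light will be seen to fluoresce in the near-infrared spectrum" after fairly short dwell times.

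Section 13.2 describes image alignment and the tumor-to-normal intensity ratio. It plans no detected proportion and no confidence interval. The documents state no confidence level, error rate or minimum acceptable detection rate.

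**The concern.** The number three is defended with a probability for an event that the decision rule does not use. Missing every subject in a cohort is one outcome; falling short of 3/3 is a different and much likelier one. The calculation also starts from a detection rate of 0.9, although detection at 10, 5 and 2.5 minutes is what the study sets out to learn. The package insert in Appendix 2 (Section 2.5) says that efficacy is not established for retention under 1 hour.

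The reverse error is not considered at all: a dwell time with poor detection can still give three positives. The dwell time that emerges goes forward to later studies, and the shortest one to pass rests on about three subjects. If Section 13.1 stands, nothing in the statistical section tells a reader of a 3/3 result how wide a range of true detection rates it leaves open.

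**Working it through.** **Inputs.** Three subjects per dwell time (Sections 8.3 and 13.1). Pass means 3/3 (Section 5). Assumed rate 0.9, from blue light (Section 13.1). My assumptions: subjects are independent with a common true per-subject detection rate p at a given dwell time; anything less than 3/3 stops progression; 95% confidence, since the plan gives no level.

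**1. The plan's own figure.** P(all three missed) = (1 - p)^3. At p = 0.9 this is 0.1^3 = 0.001, and it is smaller for p above 0.9. The stated figure is reproduced.

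**2. The event that the rule uses.** P(fewer than 3/3) = 1 - p^3. At p = 0.9: 1 - 0.729 = 0.271. So a dwell time that truly matched the blue light benchmark of 0.9 would fail to progress 27.1% of the time.

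**3. Chance that a tested dwell time passes.** P(3/3) = p^3:

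| True per-subject detection p | P(3/3) |
|---|---|
| 0.5 | 12.5% |
| 0.6 | 21.6% |
| 0.7 | 34.3% |
| 0.8 | 51.2% |
| 0.9 | 72.9% |

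**4. These are per tested cohort.** The 5 and 2.5 minute cohorts open only after the longer dwell times pass. If p were 0.5 at all three, passing all of them has probability 0.5^9 = 0.002. If p were 0.9 at 10 and at 5 minutes and 0.5 at 2.5 minutes, it is 0.729 × 0.729 × 0.125 = 0.066.

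**5. What a perfect result shows.** The exact (Clopper-Pearson) lower limit for 3/3 is (α/2)^(1/3) two-sided or α^(1/3) one-sided.
- Two-sided 95%: 0.025^(1/3) = 0.292, so the interval is 29.2% to 100%.
- One-sided 95%: 0.05^(1/3) = 0.368.
- The Wilson two-sided 95% lower limit is 43.9%.

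The choice of method moves the limit between 29% and 44%. Every version is far below 0.9 and below one half.

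**6. The tenth subject.** Section 3.1 plans 10 evaluable subjects, and three cohorts of three use nine. One more subject at the chosen dwell time would give, for 4/4, a two-sided limit of 0.025^(1/4) = 0.398. The conclusion does not change.

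**The case against.** The strongest reply is that this is a pilot and says so. Section 2.2 leaves the comparison with blue light to later randomized studies, Section 5 speaks of feasibility, and Section 5.2, which is itself headed as an efficacy section, limits the aim to showing that tumors visible under white light also fluoresce. Efficacy in Section 13.1 may carry the same narrow meaning. The tumor-to-normal ratio adds quantitative evidence beyond the yes/no count. The 0.9 is an input, not a target set for NIRF, and the 95% level used here is the reviewer's choice.

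Much of this stands, and it limits the point. It does not remove it. The primary aim is still a minimal dwell time for adequate detection, the result is carried into later studies, and the ratio analysis has no criterion that would qualify a 3/3 result. Three subjects can serve the purpose in Section 5.2; they cannot support the sentence in Section 13.1 on its ordinary meaning.

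Four stronger readings are tempting, and the documents do not support them:
- *That Section 13.1 contains an arithmetic error.* It does not; 0.001 is correct for the event it describes.
- *That the trial plans to claim parity with blue light.* No section does so.
- *That an inadequate dwell time has a 1 in 8 chance of being selected overall.* The 12.5% holds at p = 0.5 for a cohort that is actually tested. Step 4 shows that the chance through the whole sequence is lower when earlier cohorts can fail.
- *That the cohorts must be enlarged.* That would follow only if efficacy were the aim. For feasibility the size can stay.

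**Conclusion.** The point holds as a fault of inference and sample-size justification. The 0.001 does not bear on the 3/3 rule: at the assumed 0.9 a cohort falls short of 3/3 27.1% of the time, and a tested dwell time with true detection between 0.5 and 0.8 passes between 12.5% and 51.2% of the time. The best possible result, 3/3, is compatible with true detection as low as 29.2% (two-sided) or 36.8% (one-sided).

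This rests on independent subjects, a common rate within each cohort, 95% confidence, and reading the stop sentence in Section 5 as anything short of 3/3. That sentence could also be read as stopping only when none of the three fluoresces. A dwell time with p = 0.5 would then pass with probability 1 - 0.5^3 = 87.5%, so the point would be stronger.

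Should-fix: the remedy is wording and reporting, and it changes neither the conduct of the trial nor which dwell time is selected.

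**What to change.** **Section 13.1.** Replace both the 0.001 sentence and the concluding sentence on efficacy. Changing only the conclusion would leave it resting on a calculation for the wrong event. The new text should say that:
- three subjects per dwell time show feasibility only;
- blue light sensitivity at 1 hour is not assumed to hold for NIRF at short dwell times;
- a cohort that is tested passes 3/3 with probability 12.5%, 21.6%, 34.3%, 51.2% and 72.9% at true per-subject detection of 0.5, 0.6, 0.7, 0.8 and 0.9, and shorter dwell times are tested only after longer ones pass.

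**Section 13.2.** Add that the detected proportion at each dwell time will be reported with its exact two-sided 95% confidence interval (29.2% to 100% for 3/3). Limit the conclusion to feasibility, and name the selected dwell time as a candidate for later study.

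**Cost.** Two sentences replaced and one reporting line added. Section 5.2 already commits to documenting whether each tumor is detected. No more patients are needed and the progression rule is unchanged. The downside is that the stated justification becomes less favourable.

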13.2. Planned Statistical Analysis

The procedure will be digitally recorded during simultaneous acquisition of the visible (white light) image and the fluorescence image from separate cameras with precisely aligned fields of view. At any time point, both cameras record the image from the same tissue location as relayed by the cystoscope. Therefore, the images are completely spatially coordinated and the location of any feature (tumor) observed on the white light image will be known in the corresponding image recorded by the fluorescence detection camera. Accordingly, tumors visualized by the white light image should be visible in the fluorescence image as features with enhanced emission. This association thus enables us to determine if PPIX emission arising from tumors is detectable within the specified dwell time. The localized intensity of the fluorescence image will be quantified by comparing the emission arising from the tumor location to the background emission from surrounding normal tissue. The ratio

of intensity between the tumor location and the surrounding normal tissue will be used to quantify the signal strength. We will use this value for further analysis to quantify the signal strength as a function of dwell time.

13.3. Data and Safety Monitoring

Study Investigators will conduct continuous review of data and subject safety. The Investigator will submit **semi-annual** progress reports of these data to the Data Safety Monitoring Committee at the Wilmot Cancer Institute for review. The review will include for each treatment arm/dose level: the number of subjects enrolled, withdrawals, significant toxicities as described in the protocol, serious adverse events both expected and unexpected, dose adjustments, and responses observed.

The PI maintains a database of all adverse events with toxicity grade and information regarding treatment required, complications, or sequelae. The Investigator will submit a copy of the AE spreadsheet along with the Progress Report to the Data Safety Monitoring Committee at the Wilmot Cancer Institute for review. Actual review dates will be assigned when the first subject is accrued.

- Any serious adverse event that is serious, related AND unexpected must be reported within 10 calendar days to both the Safety Coordinator at the Wilmot Cancer Institute and the RSRB (see RSRB guidelines). The DSMC Chair will determine whether further action is required, and when subject safety is of concern, an interim meeting may be called.
- Serious adverse events that are related AND expected or unrelated AND unexpected will be reported to the DSMC for review at the next quarterly meeting. SAE reports are expected to include sufficient detail so that the DSMC can determine the severity, toxicity grade, expectedness, treatment required, and follow up report documenting resolution or if there are sequelae. Unless otherwise specified in the protocol, serious adverse events that require detailed reports (but not necessarily expedited) are expected, related, non-hematologic toxicities of grades 3, 4 or 5.

The Data Safety Monitoring Committee provides oversight of study progress and safety by review of accrual and events at regularly scheduled meetings. The frequency of review is determined by the size, risk and complexity of the trial, and is assigned by the Protocol Review Committee at the time of their initial review and approval. The Data and Safety Monitoring Committee will monitor all adverse event rates utilizing a cumulative spreadsheet listing of all events submitted along with progress reports by the PI. All serious adverse events that have occurred in the prior 3 months will be reviewed at the regular quarterly meeting of the DSMC in order to confirm toxicity grade, expectedness, relatedness, sequelae, follow up required, and risk to current or future subjects.

These highlights do not include all the information needed to use Cysview safely and effectively. See full prescribing information for Cysview.

Cysview (hexaminolevulinate hydrochloride), for Intravesical Solution

For bladder instillation only
Initial U.S. Approval: 2010

INDICATIONS AND USAGE

Cysview is an optical imaging agent indicated for use in the cystoscopic detection of non-muscle invasive papillary cancer of the bladder among patients suspected or known to have lesions on the basis of a prior cystoscopy. Cysview is used with the Karl Storz D-Light C Photodynamic Diagnostic (PDD) system to perform cystoscopy with the blue light setting (Mode 2) as an adjunct to the white light setting (Mode 1).

Important Limitations of Use:

- Not a replacement for random bladder biopsies or other procedures used in the detection of bladder cancer. (1.1, 1.2)

- Not for routine use. (1.1, 1.5)

DOSE AND ADMINISTRATION

Training in blue light cystoscopy with the Karl Storz D-Light C PDD system is essential prior to the use of Cysview. (2.3)

- Reconstitute Cysview powder with all 50 mL of supplied DILUENT under aseptic conditions. (2.2)

- Use solution of Cysview shortly after reconstitution. If unable to use, the solution may be stored for up to 2 hours in a refrigerator at 2°-8°C (36°-46°F) in labeled syringe. Discard after 2 hours. (2.2, 16)

- Instill 50 mL of reconstituted solution of Cysview into the emptied bladder via an intravesical catheter. Retain in the bladder for 1 hour before evaluating and performing cystoscopic examination. (2.3, 2.5)

- First perform a complete cystoscopic examination of the entire bladder under white light and then repeat the examination of the entire bladder under blue light. Record and document information about location and appearance of suspicious lesions and areas seen under both white and blue light. (2.5)

DOSE AND ADMINISTRATION

Cysview (hexaminolevulinate hydrochloride) is supplied as a kit containing:

- A 10 mL glass vial containing 100 mg powder of Cysview (hexaminolevulinate hydrochloride) for Intravesical Solution.

- A polypropylene vial containing 50 mL DILUENT for Cysview.

- One Luer Lock catheter adapter. (16)

Once reconstituted, the solution contains 2 mg/mL (0.8 mmol/L) of hexaminolevulinate hydrochloride.

CONTRAINDICATIONS

Do not use Cysview in patients with:

- porphyria,

- gross hematuria,

- BCG immunotherapy or intravesical chemotherapy within the past 30 days or known hypersensitivity to hexaminolevulinate or aminolevulinic acid derivatives. (4)

WARNINGS AND PRECAUTIONS

- Anaphylaxis: have trained personnel and therapies available. (5.1)

- Failed Detection: Cysview may not detect all malignant lesions. Always perform white light cystoscopy (Mode 1) followed by blue light cystoscopy (Mode 2). Do not biopsy with blue light only. (5.2)

- False fluorescence may occur due to inflammation, cystoscopic trauma, scar tissue or previous bladder biopsy. (5.3)

ADVERSE REACTIONS

The most common adverse reaction reported in patients who received Cysview was bladder spasms occurring in < 3% of patients, followed by dysuria, hematuria, bladder pain, procedural pain, urinary retention and headache, all occurring in 5.2% of patients. (6.1)

To report SUSPECTED ADVERSE REACTIONS, contact Photocure Inc. at [name] or FDA at [name] or www.fda.gov/medwatch.

USE IN SPECIFIC POPULATIONS

- Pregnancy Category C: No human or animal data. Use only if clearly needed. (8.1)

- Nursing mothers: No human or animal data. Exercise caution when Cysview is administered to nursing mothers. (8.3)

- Pediatric Use: Safety and effectiveness in pediatric patients have not been established. (8.4)

See 17 for PATIENT COUNSELING INFORMATION. Revised: 11/2011

FULL PRESCRIBING INFORMATION: CONTENTS

1 INDICATIONS AND USAGE

Cysview is an optical imaging agent indicated for use in the cystoscopic detection of non-muscle invasive papillary cancer of the bladder among patients suspected or known to have lesions on the basis of a prior cystoscopy. Cysview is used with the Karl Storz D-Light C Photodynamic Diagnostic (PDD) system to perform cystoscopy with the blue light setting (Mode 2) as an adjunct to the white light setting (Mode 1).

1.1 Limitations of Use

Cysview is not:

- a replacement for random bladder biopsies or other procedures used in the detection of bladder cancer [see Warnings and Precautions (5.2)].

- for routine use. The potential risks associated with repetitive exposure including sensitization and adverse effects of blue light have not been evaluated [see Warnings and Precautions (5.1)].

2 DOSAGE AND ADMINISTRATION

2.1 Recommended Dose

The recommended dose for adults is 50 mL of reconstituted solution of Cysview [see Dosage and Administration (2.2)], instilled into the bladder via a urinary catheter [see Dosage and Administration (2.3)].

2.2 Reconstitution of Cysview

Cysview is supplied as a kit containing two vials: a clear glass vial labeled as Cysview (hexaminolevulinate hydrochloride) for Intravesical Solution, containing 100 mg hexaminolevulinate hydrochloride as a powder, and a vial labeled as DILUENT for Cysview, containing 50 mL of the solvent in a polypropylene vial.

Perform all steps under aseptic conditions. Use gloves during the reconstitution procedure; skin exposure to hexaminolevulinate hydrochloride may increase the risk for sensitization to the drug.

Use a 50 mL syringe with a Luer Lock throughout the reconstitution procedure to ensure that the correct concentration (2 mg/mL) of the drug is obtained and that a stable syringe-catheter connection is made for the bladder instillation of Cysview.

Figure 1. 1. Remove the cap from the sterile 50 mL syringe and carefully label it for subsequent attachment to the syringe (step 4). Attach a needle to the syringe and withdraw 50 mL of the diluent (Figure 1).

Figure 2. 2. Penetrate the stopper of the Cysview powder vial with the needle and insert 10 mL of the diluent from the syringe into the powder vial (Figure 2).

[figure not shown]

Figure 3. 3. Without withdrawing the needle from the vial, hold the powder vial and syringe in a firm grip (Figure 3) and gently shake to dissolve of the powder in the diluent. The powder normally dissolves almost immediately.

Figure 4. 4. Withdraw all of the dissolved solution from the powder vial (10 mL) into the 50 mL syringe (Figure 4).

Figure 5. 5. Remove the needle from the powder vial, disconnect the needle from the syringe tip and discard it. Plug the syringe with the syringe cap (Figure 5). Gently mix the contents of the syringe. The reconstituted solution of Cysview is colorless to pale yellow and clear to slightly opalescent, and free from visible particles.

[figure not shown]

Figure 6. 6. Peel off the detachable portion of the label (starting at the corner marked with a black triangle) from the Cysview powder vial and affix it to the syringe containing the solution of Cysview (Figure 6). Add two hours to the present time and write the resulting expiration time and date on the syringe label.

Cysview is now reconstituted and ready for use. Instill the reconstituted solution of Cysview into the bladder. If unable to administer the solution shortly after reconstitution, the solution may be stored for up to 2 hours in a refrigerator at 2°-8°C (36°-46°F) in the labeled syringe. If not used within 2 hours, discard the solution. [see Dosage and Administration (2.2) and How Supplied/Storage and Handling (16)].

